2.6.1 Secondary endpoints

Relapse-Free Survival (RFS)

RFS is defined as the time from start of treatment to the date of first documented hematologic relapse or death due to any cause, whichever occurs first. RFS will be censored if no RFS event is observed before the first to occur between: (i) the analysis cut-off date, (ii) the date when a new anti-neoplastic therapy or a donor lymphocyte infusion (DLI) is started, and (iii) lost to follow-up or withdrawal of consent. The censoring date will be the date of the last adequate response assessment prior to cut-off/start of new anti-neoplastic therapy or DLI. The handling of intercurrent events will be the same as the primary estimand.

RFS will be analyzed in the FAS population and the RFS distribution will be estimated using the Kaplan-Meier method. Kaplan-Meier curves, medians and 95% confidence intervals of the medians will be presented for each dose cohort.

The following events could occur during the study and may affect the interpretation of the results:

- Start of donor lymphocyte infusions (DLI) or a new anti-neoplastic therapy: For a participant without an event before the time he/she receives any DLI or further anti-cancer therapy, RFS would be censored at the date of the last adequate assessment prior to start of DLI or further anti-neoplastic therapy.
- Stopping study treatment (including due to toxicities): All events will be taken into account when they occur, regardless of any study treatment interruption or permanent discontinuation.
- Discontinuation from study due to lost to follow-up or withdrawal of consent: For a participant without an event prior to discontinuation due to lost to follow-up or withdrawal of consent, RFS will be censored at the last adequate assessment date.

In case of two or more missing assessments prior to documented relapse or death, RFS will be censored at the last adequate response assessment prior to the documentation of relapse or death. The rule to determine whether there are two missing assessments is described in Section 2.6.3.

The RFS censoring reason will be summarized as:

- 1. Ongoing without event
- 2. New anti-neoplastic therapy
- 3. Donor lymphocyte infusions
- 4. Withdrew consent
- 5. Lost to follow-up
- 6. Event documented after two or more missing response assessments

GvHD-free/relapse-free survival (GRFS) - Not assessable

GRFS is defined as the time from start of treatment to the date of first documented occurrence or worsening of treatment emergent grade III or IV aGvHD or moderate to severe cGvHD requiring initiation of systemic treatment, hematologic relapse, or death due to any cause, whichever occurs first. GRFS will be censored if no GRFS event is observed before the first to occur between: (i) the analysis cut-off date, (ii) the date when a new anti-neoplastic therapy, or a donor lymphocyte infusion (DLI) is started, and (iii) lost to follow-up or withdrawal of consent.

Novartis	Confidential	Page 25 of 35
SAP – Amendment 1		CMBG453F12201

The censoring date will be the date of the last adequate response assessment prior to cut-off/start of new anti-neoplastic therapy or DLI.

GRFS will be analyzed in the FAS population and the GRFS distribution will be estimated using the Kaplan-Meier method. Kaplan-Meier curves, medians and 95% confidence intervals of the medians will be presented for each dose cohort.

The following events could occur during the study and may affect the interpretation of the results:

- Start of donor lymphocyte infusions (DLI) or a new anti-neoplastic therapy: For participant without an event before the time he/she receives any DLI or further anti-cancer therapy, GRFS will be censored at the date of the last adequate assessment prior to start of DLI or further anti-neoplastic therapy.
- Stopping study treatment (including due to toxicities): All events will be taken into account when they occur, regardless of any study treatment interruption or permanent discontinuation.
- Discontinuation from the study due to lost to follow-up or withdrawal of consent: For participants without an event prior to discontinuation due to lost to follow-up or withdrawal of consent, GRFS will be censored at the last adequate assessment date.

In case of two or more missing assessments prior to documented relapse or death or treatment emergent grade III or IV aGvHD, or moderate to severe cGvHD requiring initiation of systemic treatment, GRFS will be censored at the last adequate response assessment prior to the documentation of the event. The rule to determine whether there are two missing assessments is described in Section 2.6.3.

The GRFS censoring reason will be summarized as:

- 1. Ongoing without event
- 2. New anti-neoplastic therapy
- 3. Donor lymphocyte infusions
- 4. Withdrew consent
- 5. Lost to follow-up
- 6. Event documented after two or more missing response assessments

MRD conversion rate based on central MFC-MRD assessment from BMA

MRD conversion rate is defined as the proportion of participants with centrally confirmed MRD+ status at baseline converting to MRD- as per central review within the first 6 cycles of study treatment. MRD-negativity will be defined as frequency of LAIP below 0.1%, as determined by a MFC-AML MRD assay by central review. A total of 4 post-baseline bone marrow aspirate or biopsy assessments is planned to be performed during the first 6 cycles of treatment (on Cycle 2 Day 1, Cycle 3 Day 1, Cycle 4 Day 1 and Cycle 7 Day 1). A participant with at least one post-baseline MRD-negativity regardless of the subsequent MRD assessments and regardless of treatment interruption or discontinuation. Only MRD samples collected before start of new anti-neoplastic therapy or DLI will be considered for this analysis.

Novartis	Confidential	Page 26 of 35
SAP – Amendment 1		CMBG453F12201

MRD conversion rate will be analyzed in the FAS population and will be provided with exact 95% confidence interval for each dose cohort.

Local MRD assessment will be listed including chimerism data used for inclusion criteria.

2.6.2 Statistical hypothesis, model, and method of analysis

No formal statistical tests will be performed for any of the secondary efficacy endpoints and hence no multiplicity adjustment will be applied.

2.6.3 Handling of missing values

For RFS analysis, the rule to determine whether there are two missing assessments will be based on the distance between the last adequate response assessment date and the event date. If the distance is larger than threshold D_2 then the analysis will assume that there are two missing assessments. This threshold D_2 is defined as two times the protocol specified interval between the response assessments plus the allowed window around the assessments. The protocol defines that response assessment has to be done at least at the time of bone marrow assessments that are to be done on Day 1 at Cycles 2, 3 and 4 (4 weeks +/- 1 week), then every 3 cycles (12 weeks +/- 2 weeks) until Cycle 13 and every 6 months (24 weeks +/- 4 weeks) thereafter. Therefore, for the cycles until Cycle 4, any distance larger than $D_2 = 2*5$ weeks = 10 weeks (2.5 months) between last adequate assessment and the event means that there are two missing assessments. For the period between Cycle 4 and Cycle 13, any distance larger than $D_2 = 2*14$ weeks = 28 weeks (7 months) means that there are two missing assessments. And finally, for the period beyond Cycle 13, any distance larger than $D_2 = 2*28$ weeks = 56 weeks (1 year) means that there are two missing assessments.

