- As applicable, Pregnancy Outcomes Reporting Consent for female participants
- A molecular pre-screening informed consent to allow shipping of local bone marrow aspirate collected as per routine practice to a designated central laboratory for central analysis

Women of childbearing potential must be informed that taking the study treatment may involve unknown risks to the fetus if pregnancy were to occur during the study and agree that in order to participate in the study, they must adhere to the contraception requirements.

A copy of the approved version of all consent forms must be provided to Novartis after IRB/IEC approval.

8 Visit schedule and assessments

Assessment schedule Table 8-1 and Table 8-2 lists all of the assessments when they are performed. All data obtained from these assessments must be supported in the participant's source documentation.

- Each treatment cycle is 28 days.
- Screening evaluations should be performed within ≤ 28 days of Cycle 1 Day 1 (except
 for the pregnancy test which has to be performed within 72 hours before the first dose).
 Lab tests results must be provided within a maximum of 7 days prior to start of
 treatment.

Participants should be seen for all visits/assessments as outlined in the assessment schedule (Table 8-1 and Table 8-2) or as close to the designated day/time as possible. Missed or rescheduled visits should not lead to automatic discontinuation. Participants who prematurely discontinue the study for any reason should be scheduled for a visit as soon as possible, at which time all of the assessments listed for the final visit will be performed. At this final visit, all dispensed investigational product should be reconciled, and the adverse event and concomitant medications recorded on the CRF.

During the course of the study visits, test and/or procedures should occur on schedule whenever possible. A visit window of +/- 3 days is allowed for study procedures (including treatment administration after C1D1). See Section 6.1 and Section 6.5 for details on study treatment, dosing and permitted dose delays. A visit window of +/- 7 days will be allowed for BMA procedures. Further, a maximum of 7 days is allowed between BMA efficacy, hematology assessments, and extramedullary disease assessments (if applicable) of the same visit.

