12.4.4 Handling of missing values not related to intercurrent event

For the determination of the absence of evidence of hematologic relapse (ie, no evidence of bone marrow blasts ≥5%; no evidence of reappearance of blasts in the blood; no evidence of development of extramedullary disease) after 6 cycles of treatment, only the response assessment performed at Cycle 7 Day 1 or the response assessment performed 6 months after starting the study treatment is considered.

An adequate response assessment is considered any disease assessment indicating response status apart from "unknown" or "not done". Evaluation of response relies on bone marrow, peripheral blood, and extramedullary disease assessment. In case of missing data for the full assessment required to qualify for a given response or in case of a more than 7 days difference between bone marrow aspirate/biopsy assessments and hematology assessments of the same visit, the overall assessment "unknown" was assigned unless relapse was seen in at least one compartment (i.e. bone marrow or blood).

A participant will be considered with no evidence of hematologic relapse if an adequate response assessment indicates a complete remission (CR) or a complete remission with incomplete hematologic recovery (CRi) response; and even if one or several inadequate response assessments ("unknown" or "not done") have been documented prior to the current adequate response assessment.

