- 3. Treatment of interest: Treatment with sabatolimab or sabatolimab in combination with azacitidine taken for the entire study duration post aHSCT. One estimand for each of the two treatments of interest (sabatolimab in monotherapy and sabatolimab in combination with azacitidine) will be considered.
- 4. Handling of intercurrent events:

- Failure to complete 6 cycles of treatment due to death for any reason or relapse: a participant who dies or has a relapse before completing 6 cycles of treatment will be considered as a non-responder (composite variable strategy).
- Start of donor lymphocyte infusions (DLI) or a new anti-neoplastic therapy before completing 6 cycles of study treatment: a participant who starts a DLI or a new antineoplastic therapy before completing 6 cycles of treatment will be considered as a non-responder (composite variable strategy).
- Failure to complete 6 cycles of treatment due to reasons other than relapse and death for any reason (including due to adverse events, graft vs. host disease for example): all participants with an adequate response assessment (other than "unknown" response) will be taken into account regardless of any study treatment interruption or permanent discontinuation; for a participant who stops the study due to reasons other than relapse or death, we will ask the participant to perform a response assessment 6 months after starting study treatment; a participant with no evidence of hematologic relapse 6 months after starting treatment will be considered a responder (treatment policy strategy).
- 5. Summary measure for the primary efficacy estimand is the proportion of participants with no evidence of hematologic relapse with its exact 95% confidence interval for each of the two study treatment of interest: sabatolimab in monotherapy and sabatolimab in combination with azacitidine. The trial will be successful if at least one of the treatments of interest (sabatolimab monotherapy or sabatolimab in combination with azacitidine) meets both statistical and clinical significance.

The **primary safety estimand for adolescent participants** included in this study is described by the following attributes:

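### The SAP's elapsed-time test for two missed assessments in RFS does not say which date sets the threshold, and misclassifies gaps that cross a change in visit interval under either reading

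*SAP*

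**What the plan says.** SAP 2.6.1 censors RFS at the last adequate response assessment when two or more assessments are missing before a relapse or death. SAP 2.6.3 gives the test. The rule for deciding "whether there are two missing assessments will be based on the distance between the last adequate response assessment date and the event date". The threshold, called D2, is built from the visit interval and its window, and it has three tiers:

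- first tier: "Therefore, for the cycles until Cycle 4, any distance larger than" 10 weeks;
- second tier: "For the period between Cycle 4 and Cycle 13, any distance larger than" 28 weeks;
- third tier: beyond Cycle 13, more than 56 weeks.

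The schedule behind these figures is Day 1 of Cycles 2, 3 and 4 (4 weeks, window 1 week), "then every 3 cycles (12 weeks +/- 2 weeks) until Cycle 13 and every 6 months (24 weeks +/- 4 weeks) thereafter". The protocol's own window is narrower. Its Section 8 states: "A visit window of +/- 7 days will be allowed for BMA procedures".

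Protocol 12.5.1, which defines RFS and its censoring, has no rule on missed assessments. SAP Section 4, on changes to protocol-specified analyses, is marked as not applicable. SAP Table 1-1 keeps RFS for the final report.

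**The concern.** A gap has two ends, and they can lie in different tiers. The SAP does not say which end selects the threshold. It names Cycle 4 in two tiers and does not place Cycle 13 Day 1. Two programmers following the text could therefore treat the same relapse differently, one as an event and one as censored.

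The larger question is whether either reading gives the intended result. The rule is meant to censor after two missed visits and to keep the event after one. A single interval doubled can do that only while the interval is constant. The planned interval changes from 4 to 12 weeks at Cycle 4 and from 12 to 24 weeks at Cycle 13. The first change leads directly to Cycle 7 Day 1, the primary efficacy visit, where by protocol 12.4.4 "only the response assessment performed at Cycle 7 Day 1 or the response assessment performed 6 months after starting the study treatment is considered". RFS is reported as Kaplan-Meier curves and medians in small cohorts (about 8 and 12 planned in the run-in), so a single reclassified relapse can be visible.

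**Working it through.** **Reproducing the thresholds.** D2 = 2 × (interval + window), with the SAP's inputs:

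- 2 × (4 + 1) = 10 weeks
- 2 × (12 + 2) = 28 weeks
- 2 × (24 + 4) = 56 weeks

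All three match. With the protocol's 1-week marrow window throughout, the same formula gives 10, 2 × 13 = 26 and 2 × 25 = 50 weeks.

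**Planned visits.** Protocol 8.3.1, with 28-day cycles and no delays, puts post-baseline assessments at weeks 4 (C2D1), 8 (C3D1), 12 (C4D1), 24 (C7D1), 36 (C10D1), 48 (C13D1), 72 (C19D1) and 96. Eight visits give 8 × 7 / 2 = 28 pairs of last adequate assessment and later event. For each pair I compared the flag (gap > D2) with whether two or more visits were actually missed.

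**Within one tier the rule works.** One miss gives gaps of 8, 24 or 48 weeks, none above 10, 28 or 56. Two misses give 12, 36 or 72, all above.

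**Across a change of interval it does not.** The pairs below fail wherever C4D1 and C13D1 are placed.

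| Reading | Pair | Visits missed | Gap (weeks) | D2 | Result |
|---|---|---|---|---|---|
| Last assessment sets tier | C3D1 to C7D1 | 1 | 24 − 8 = 16 | 10 | censored |
| Last assessment sets tier | C10D1 to C19D1 | 1 | 72 − 36 = 36 | 28 | censored |
| Event sets tier | C2D1 to C7D1 | 2 | 24 − 4 = 20 | 28 | counted |
| Event sets tier | C3D1 to C10D1 | 2 | 36 − 8 = 28 | 28 | counted |
| Event sets tier | C7D1 to C19D1 | 2 | 72 − 24 = 48 | 56 | counted |

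If each boundary visit is placed by the interval concerned (the one after the last assessment, or the one before the event), the errors are 2 of 28 and 3 of 28. Other placements give up to 5 of 28 wrongly censored under the first reading and up to 6 of 28 wrongly counted under the second.

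**Off treatment.** The tiers are named by cycle, and the SAP does not say how they apply after treatment ends. Protocol 8.3.1 and 9.1.1.2 put marrow assessments at 6-month intervals, while the follow-up cells of Tables 8-1 and 8-2 repeat the cycle-based schedule. As an assumed example, take an end-of-treatment marrow at week 10 and a relapse at week 34, a gap of 24 weeks. The last-assessment reading censors it (24 > 10) and the event reading counts it (24 < 28). On a 24-week follow-up schedule nothing was missed; on the cycle-based one the week-24 visit was. For participants who stop early SAP 1.2.1 adds that "we will ask the participant to perform a response assessment 6 months after starting study treatment", which is a further date to place.

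**Checking a replacement.** Let the last adequate assessment set D2 as the sum of the next two scheduled intervals plus their windows.

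| Last adequate assessment | D2, SAP windows | D2, 1-week window | Gap with one miss | Gap with two misses |
|---|---|---|---|---|
| Treatment start | 4+4+1+1 = 10 | 10 | 8 | 12 |
| C2D1 | 4+4+1+1 = 10 | 10 | 8 | 20 |
| C3D1 | 4+12+1+2 = 19 | 18 | 16 | 28 |
| C4D1 | 12+12+2+2 = 28 | 26 | 24 | 36 |
| C7D1 | 12+12+2+2 = 28 | 26 | 24 | 48 |
| C10D1 | 12+24+2+4 = 42 | 38 | 36 | 60 |
| C13D1 onward | 24+24+4+4 = 56 | 50 | 48 | 72 |

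In every row the one-miss gap is at or below D2 and the two-miss gap is above it, with either set of windows.

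**The case against.** The strongest reply is that an elapsed-time rule is an openly stated approximation, and that one sentence naming the tier date would be enough. RFS carries no formal test (SAP 2.6.2), all response assessments are listed (SAP 2.6), and events censored under this rule have their own censoring reason, so affected participants can be found. The study also stopped early. All of this stands, and it keeps the point minor. But naming the tier date does not remove the errors, because each reading has its own.

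Three stronger inferences are tempting.

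- A reader might infer that the rule censors a fully compliant participant who relapses at C7D1 after an adequate C4D1. That gap is 12 weeks, so it happens only if C4D1 sits in the 10-week tier. SAP 2.6.3 derives D2 from the scheduled interval and names a period between Cycle 4 and Cycle 13. Both point to 28 weeks for that gap. It is a reason to state the boundary, not an established result.
- A reader might see a contradiction with SAP 2.6.1, which says of stopping treatment: "All events will be taken into account when they occur, regardless of any study treatment interruption or permanent discontinuation". That sentence concerns treatment discontinuation. The missed-assessment rule is a separate, explicit exception.
- A reader might infer a material bias in the RFS curve. The documents do not say how many participants missed visits at these transitions. The 28 pairs are unweighted and cover only events found at planned visits. Deaths and promptly evaluated suspected relapses fall outside them.

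The difference in windows also adds little. Using 26 and 50 weeks changes one of the 28 pairs (C3D1 to C10D1), and only under the event reading.

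**Conclusion.** The point holds as a minor one. As written, SAP 2.6.3 leaves the tier date open, and each available reading gives wrong event or censoring decisions where the visit interval changes: at least 2 of 28 planned pairs wrongly censored if the last assessment sets the tier, or at least 3 of 28 wrongly counted if the event does. The direction of error therefore depends on an unstated choice. Off treatment, the tiers are undefined and the protocol's schedule is inconsistent, so the number of missed visits cannot be settled from the text.

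These counts assume undelayed 28-day cycles and events detected at planned visits. They describe the rule, not the frequency of the problem in the data, which is unknown.

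**What to change.** In SAP 2.6.3, let the last adequate assessment set the threshold, and define D2 as the sum of the two scheduled intervals that follow it plus their windows. With the SAP's windows this is 10 weeks (treatment start or C2D1), 19 (C3D1), 28 (C4D1 and C7D1), 42 (C10D1) and 56 (C13D1 onward). With the protocol's 7-day marrow window it is 10, 18, 26, 38 and 50. State which windows apply. Listing thresholds by visit also settles where C4D1 and C13D1 belong.

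Counting missed scheduled visits gives the same answer at planned visits. If that route is taken, use the protocol's own rules for delayed cycles rather than shifting every date. Section 8 keeps assessments on calendar days from Day 1 of the previous cycle and shifts the schedule on resumption in the combination cohort. Section 8.3.1 returns to the original plan after a delayed evaluation.

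In addition:

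- use treatment start as the anchor when there is no adequate post-baseline assessment;
- reconcile the off-treatment assessment schedule and apply the same definition to it;
- record the rule in SAP Section 4, since protocol 12.5.1 does not contain it;
- optionally, add one sensitivity Kaplan-Meier curve that counts all documented relapses and deaths.

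The cost is SAP wording and a slightly longer derivation, plus one output if the sensitivity curve is added. No new data are needed.

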For the calculation of the dose intensity and relative dose intensity, the duration in days from first to last cycle initiated will be calculated as follow: date of last exposure - date of first administration of study treatment (combination) + 1.

Thus, this derivation will be irrespective of date of death or last contact date (i.e. it should not be truncated to the date of death or date of last contact date).

Study day

The study day, describes the day of the event or assessment date, relative to the reference start date (start date of study treatment).

The study day is calculated as follows:

- The date of the event (visit date, onset date of an event, assessment date etc.) reference start date + 1 if event is on or after the reference start date;
- The date of the event (visit date, onset date of an event, assessment date etc.) reference start date if event precedes the reference start date.

The reference start date for safety assessments (e.g. adverse event onset, laboratory or ECG assessment, vital sign measurement etc.) is the start of study treatment. The same reference start date will be used for efficacy (e.g. response assessment, time-to-event endpoints).

The study day will be displayed in the data listings. If an event starts before the reference start date, the study day displayed on the listing will be negative.

Time unit

A year length is defined as 365.25 days. A month length is 30.4375 days (365.25/12). If duration is reported in months, duration in days will be divided by 30.4375. If duration is reported in years, duration in days will be divided by 365.25.

Baseline

For efficacy evaluations, the last non-missing assessment, including unscheduled assessments on or before the date of start of study treatment is taken as "baseline" value or "baseline" assessment.

For safety evaluations, the last available assessment including unscheduled assessments on or before the date of start of study treatment is taken as "baseline" assessment.

If participants have no value as defined above, the baseline result will be missing.

Laboratory parameter derivations

If laboratory values are provided as '<X' (i.e. below limit of detection) or '>X', prior to conversion of laboratory values to SI unit, these numeric values are set to X.

The following rules will be applied to derive the WBC differential counts when only percentages are available for a xxx differential

xxx count = (WBC count) * (xxx %value / 100)

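### SAP 2.6.3 attributes windows of 2 and 4 weeks to the protocol, whose only bone marrow window is 7 days; on the SAP's own rule the later RFS censoring limits are 26 and 50 weeks, not 28 and 56

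*SAP*

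**What the plan says.** SAP 2.6.1 censors RFS at the last adequate response assessment when a relapse or death is documented after two or more missing assessments. SAP 2.6.3 turns this into a distance rule: "This threshold D_2 is defined as two times the protocol specified interval between the response assessments plus the allowed window around the assessments".

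The inputs are presented as protocol content ("The protocol defines that response assessment has to be done at least at the time of bone marrow assessments"). They come in three tiers: "Day 1 at Cycles 2, 3 and 4 (4 weeks +/- 1 week"), and "then every 3 cycles (12 weeks +/- 2 weeks) until Cycle 13 and every 6 months (24 weeks +/- 4 weeks) thereafter". The later limits follow:

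- Cycle 4 to Cycle 13: "any distance larger than $D_2 = 2*14$ weeks = 28 weeks (7 months) means that there are two missing assessments"
- Beyond Cycle 13: "any distance larger than $D_2 = 2*28$ weeks = 56 weeks (1 year) means that there are two missing assessments"

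The protocol's statement on the marrow window is in Section 8 (Visit schedule and assessments): "A visit window of +/- 7 days will be allowed for BMA procedures". It makes no distinction between early and late visits. Other study procedures have a narrower window of 3 days either side.

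SAP Table 1-1 keeps RFS for the final CSR, so the rule is in use. SAP Section 4 declares no change to protocol-specified analyses.

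**The concern.** The rule depends on the protocol's interval and the protocol's allowed window. If the window is wider than the protocol allows, the limit is longer than the rule implies. Some events that follow two missed assessments are then counted as events at their late documentation date, not censored at the last adequate assessment. In a Kaplan-Meier analysis of a few participants, one such reclassification can move the curve or the median.

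The bracketed equivalents raise a second question. SAP 5.1 says "A month length is 30.4375 days (365.25/12") and that a year is 365.25 days. If a bracket does not match its limit in weeks, the text offers two cut-offs for the same tier.

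**Working it through.** **Inputs.** Intervals of 4, 12 and 24 weeks and windows of 1, 2 and 4 weeks come from SAP 2.6.3. The marrow window of 7 days (1 week) and the cycle length of 28 days come from Protocol Section 8. A month of 30.4375 days and a year of 365.25 days come from SAP 5.1.

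**Reproducing the SAP.** The defining sentence can be read in two ways.

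- 2 × (interval + window): 2 × (4 + 1) = 10; 2 × (12 + 2) = 28; 2 × (24 + 4) = 56 weeks. All three stated limits are reproduced.
- 2 × interval + window: 8 + 1 = 9; 24 + 2 = 26; 48 + 4 = 52 weeks. None is reproduced.

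The SAP therefore means the first reading.

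**With the protocol's window of 1 week.**

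| Period | SAP limit | 2 × (interval + 1) | Difference |
|---|---|---|---|
| To Cycle 4 | 10 weeks (70 days) | 2 × 5 = 10 weeks (70 days) | 0 |
| Cycle 4 to 13 | 28 weeks (196 days) | 2 × 13 = 26 weeks (182 days) | 2 weeks |
| Beyond Cycle 13 | 56 weeks (392 days) | 2 × 25 = 50 weeks (350 days) | 6 weeks |

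**Check on meaning.** Suppose the last adequate assessment was done 7 days early. The window of the second assessment after it closes 7 days after that assessment's planned date. The span is 1 + 24 + 1 = 26 weeks on the 12-week schedule and 1 + 48 + 1 = 50 weeks on the 24-week schedule. These are maxima. Within one schedule period, a later event must follow two missed assessments.

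**If the late interval is 6 calendar months.** Six months is 365.25 / 2 = 182.625 days (26.09 weeks). The limit is 2 × (182.625 + 7) = 379.25 days, or about 54.2 weeks. That is below 56 weeks by 392 − 379.25 = 12.75 days.

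**The bracketed equivalents.** On a 28-day month, 70 / 28 = 2.5 and 196 / 28 = 7, which match the first two brackets. The third does not fit: 392 / 28 = 14 such months, and 392 / 365.25 = 1.07 years. Read as a year, the third tier has a cut-off of 365 days; read in weeks, 392 days. The gap is 27 days.

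**The case against.** A reader might infer that the SAP has made an arithmetic error. It has not: its limits follow exactly from the windows it states. The fault is in the windows, which are attributed to the protocol but are not found there.

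A reader might also infer that all three month or year equivalents are wrong under SAP 5.1. The first two fit a 4-week month, a convention that the same SAP sentence uses when it equates 6 months with 24 weeks and that Protocol 9.1.1.2 uses when it equates 3 months with 12 weeks. Only the equation of 56 weeks with one year is a real conflict.

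The strongest objection is that shorter limits can misclassify in the other direction. Protocol 8.3.1 describes the late marrow schedule in months, while the assessment tables use every 6 cycles. On calendar months, a participant who misses one assessment and attends the next on time is at 12 × 30.4375 = 365.25 days. A limit of 350 days would then wrongly declare two missed assessments. Similarly, Protocol Section 8 shifts the combination cohort's schedule when delayed treatment resumes. A participant assessed at Cycle 7, missing Cycle 10 and attending Cycle 13 after one 28-day delay is at 24 + 4 = 28 weeks with a single miss. A limit of 182 days would censor that participant; the SAP's limit, which must be exceeded, would not.

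Both points stand as conditions on the correction: the interval must be settled, and shifted schedules respected. They do not justify the present text, because the SAP gives neither as its reason and declares no departure from the protocol. It is also true that the protocol's own RFS definition (12.5.1) has no missed-assessment rule, so longer limits keep more observed events. That could support a deliberate choice, but the SAP does not present one.

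**Conclusion.** The inconsistency is real and minor. The limits of 28 and 56 weeks do not follow from the protocol's 7-day marrow window under the SAP's own rule. That window gives 26 weeks, and 50 weeks if the late interval is 24 weeks or about 54 weeks if it is 6 calendar months. The 10-week limit is correct. Equating 56 weeks with one year leaves two cut-offs for the last tier.

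The conclusion that the limits are too long holds within one schedule period with an unshifted schedule. Where a gap spans a change of interval, the SAP does not say which tier governs, and nothing is claimed here for that case.

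A reader might infer that RFS results are known to be distorted. The documents do not support that. They do not give the number of events in the affected bands, and in a study stopped early it may be zero or one. RFS is secondary, has no formal test (SAP 2.6.2), and all response assessments will be listed (SAP 2.6), so the gaps can be inspected.

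**What to change.** In SAP 2.6.3:

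- Replace the windows of 2 and 4 weeks with the protocol's 7 days.
- State that the interval beyond Cycle 13 is 24 weeks (6 cycles), or use 6 calendar months throughout.
- Give the limits once, in days: 70, 182, and then 350 for a 24-week interval or about 380 for 6 calendar months.
- Where combination-cohort cycles were delayed, count scheduled visits from the shifted schedule.
- Delete the month and year equivalents.

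If the sponsor intends the wider windows, it should keep them as a SAP choice, give the reason, record it in SAP Section 4 and stop describing them as protocol-defined. The single expression in days is needed in that case too.

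The cost is a wording change and the limits in the RFS program, best made before database lock and without reference to which participants fall in the bands. The downside is that an RFS event may become a censored observation.
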